1.2.18 Ethics Review

Ethics approval was granted on June 9, 2022, by the "Commissie voor Ethiek" at AZ Alma, after deliberation at their meeting on June 8, 2022.

1.2.19 Completion Date

Planned: September 30, 2022.

Actual: December 23, 2022.

1.2.20 Summary of Results

Date of posting of results summaries: December 26, 2022 (within study protocol).

Date of the first journal publication of results: Not yet achieved.

[figure not shown]
URL: Not (yet) applicable.

Baseline characteristics:

- Group 1 (eTEP): EHS Registry: BEGZ, BEHA, BEHB, BEJR, BEJS, BEJT, BEJW, BEJX, BEJZ, BEKA, BEKB, BEKC, BEKG, BEKH, BEKI, BEKJ, BEKK, BEKK, BEKM, BELE, BELF, BELG, BELH, BELI, BELJ, BELK, BELL, BEOD, BETJ, BETK.
- Group 2 (Open RS): EHS Registry: BELN, BELO, BELQ, BELR, BELS, BELT, BELU, BELV, BELV, BELY, BEOF, BEOH, BEOO, BEPV, BEPX, BEPY, BEPZ, BEQA, BEQF, BEQG, BEQJ, BEQK, BEQQ, BEQR, BEQS, BEQT, BEQV, BEQX, BETN, BETO.

Participant flow (see also participant flowchart on next page):

Date	Group 1	Group 2
June 9, 2022	23 participants	23 participants
June 13, 2022	24 participants	24 participants
June 17, 2022	25 participants	25 participants
June 20, 2022	26 participants	26 participants
June 21, 2022	27 participants	27 participants
July 11, 2022	28 participants	28 participants
August 30, 2022	30 participants	30 participants

Adverse events:

- Three conversions were needed in group 1 (eTEP) because no adequate visualization could be achieved (1 participant) or because the diastasis was deemed to large to be appropriately closed endoscopically (2 participants)
- Observed complicationa according to the Clavien-Dindo (CD) classification [3]:
 During hospital stay in the eTEP group: 1x CD I, 12x CD II.

 During hospital stay in the Open RS group: 4x CD I, 10x CD II, 4x CD IIIb.

 After discharge until 30 days in the eTEP group: 5x CD I, 1x CD II, 2x CD IIIa, 1x CD IIIb.

 After discharge until 30 days in the Open RS group: 5x CD I, 1x CD II, 5x CD IIIa, 4x CD IIIb.

Outcome measures: See brief summary.

URL protocol files: Not applicable.

Brief summary:

- Median length of hospital stay was longer in the open RS group.
- Median duration of patient-controlled analgesia was longer in the open RS group.
- Switch to only oral analgesics took longer in the open RS group.
- No significant difference in 'comparable parameter'* for postoperatively administered analgesics irrespective of PCA between both groups.
- No significant difference between the presence of prescription opioids at discharge.
- Median duration of surgery (skin-to-skin time) was significantly shorter in the open RS group.
- Need for drainage (postoperative drain inserted during primary surgery) was significantly greater in the open RS group.
- No early recurrences were found in both groups (postoperative consultation at approximately one month after surgery).
- Bulging of the abdominal midline was seen in 11 participants in the eTEP group and was not seen in the open RS group, this difference was statistically significant.

*Comparable parameter: Types of analgesics were divided into three categories. Category 1 contained only paracetamol, category 2 contained all non-steroidal anti-inflammatory drugs, and category 3 consisted of all opioids. A combination of active substances (in one analgesic) of which at least one was an opioid was seen as category 3. For each participant the absolute amount of analgesics in each category was calculated between postoperative day one and the day before discharge, this amount was divided by the amount of days between postoperative day one and the day before discharge.

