1.2.16 Primary Outcomes

- Outcome name: Length of hospital stay

Method of measurement: Time (days) spent within the hospital Timepoint: Start at day of operation (day zero) until day of discharge

Outcome name: Postoperative pain management

Method of measurement: Modality (type, generic name), duration (days), dosage (grams or

milligrams) and frequency (times per day) of analgesics administration

Timepoint: During hospital stay

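### The only analgesic-amount result appears to leave out drug given by PCA, so its null finding cannot be read as equal opioid or total analgesic use

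*Protocol*

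**What the plan says.** Section 1.2.16 lists postoperative pain management as a primary outcome, observed during the hospital stay. Its measurement line begins "Method of measurement: Modality (type, generic name), duration (days), dosage (grams or" and goes on to milligrams and frequency of administration. PCA is not excepted.

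The brief summary in section 1.2.20 gives four results that bear on the point. On PCA it says: "Median duration of patient-controlled analgesia was longer in the open RS group". It reports the same direction for median stay and for the time until patients were on oral drugs alone. The one result on amount is: "No significant difference in 'comparable parameter'* for postoperatively administered analgesics irrespective of PCA between both groups".

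The footnote to 1.2.20 defines the comparable parameter. Analgesics fall into three categories: paracetamol, non-steroidal anti-inflammatory drugs, and opioids. For the last, "category 3 consisted of all opioids". For the numerator, "the absolute amount of analgesics in each category was calculated between postoperative day one and the day before discharge". For the denominator, "this amount was divided by the amount of days between postoperative day one and the day before discharge". The footnote does not mention PCA.

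The protocol does not name the PCA drug. It gives no PCA dose or duration, no length of stay in days, and no estimate, interval or p-value for any of these comparisons.

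**The concern.** The comparable parameter is the only reported result that carries the dosage element of the primary pain outcome. If drug delivered by the pump is not in its numerator, the result is narrower than the outcome it summarises, and the opioid category does not hold what its definition says it holds.

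The omission would not be neutral by default, because the summary itself reports that use of the omitted route differed between groups. A finding of no significant difference in what remains would then say nothing about whether total opioid or total analgesic use differed. A reader who takes the summary at face value would conclude that analgesic amount was similar after the two operations, in a study whose stated aim is a superiority comparison that includes pain management.

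**Working it through.** No sample size, power or effect figure attaches to this point, so there is no figure of the plan's to reproduce. The check has two parts.

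**1. Do the statements fit together?**

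| Place | What it covers | PCA |
|---|---|---|
| 1.2.16 | Type, duration, dosage and frequency of analgesics during the stay | No exception |
| 1.2.20, footnote | Every opioid, amount per day | No exception |
| 1.2.20, result on amount | The comparable parameter | Qualified as irrespective of PCA |
| 1.2.20, result on PCA | Duration only | Longer in open RS |

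The qualifier has two possible meanings.

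- *PCA drug is left out.* This is the more natural reading. PCA has its own line, reported by duration only, and the qualifier would add little if pump drug were already counted. If the PCA drug is an opioid, the footnote's definition of category 3 is then wrong. Whatever the drug is, the result does not cover the dosage part of 1.2.16.
- *Participants are compared whether or not they had PCA, with pump drug counted.* The statements then agree, but nothing in the text tells the reader so.

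**2. If PCA drug is left out, which way does the result move?**

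Assumptions, none of them given in the protocol: discharge on day L; PCA runs for p calendar days counted from the day of operation (day 0); the amount of drug per PCA day, d, is equal in both groups.

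- Window, from postoperative day one to the day before discharge: L − 1 days.
- PCA days inside the window: min(p, L) − 1, because day 0 lies outside it.
- Amount omitted per day: d × (min(p, L) − 1) / (L − 1).

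Illustration with eTEP at L = 3 and p = 2, so the share of the window on PCA is 1/2 = 0.50. Open RS has p = 3 throughout:

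| Open RS, L | Share of window on PCA | Under-count relative to eTEP |
|---|---|---|
| 4 | 2/3 = 0.67 | larger |
| 5 | 2/4 = 0.50 | equal |
| 6 | 2/5 = 0.40 | smaller |

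In all three rows open RS has more PCA days in the window (2 against 1) and a longer stay, as the summary reports. The sign of the difference still changes.

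A grid of whole-day combinations was also run: eTEP L from 2 to 6, open RS L up to 8, with both stay and PCA longer in open RS. It has 280 combinations. The omitted share was larger in open RS in 205, equal in 25 and smaller in 50 (205 + 25 + 50 = 280). These counts are not probabilities. They show only that longer PCA does not by itself fix the direction.

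**The case against.** The strongest reply is that exclusion of PCA drug is inferred, not stated. The qualifier can mean regardless of PCA use, the definition contains no exception, and the PCA drug is not said to be an opioid. Even if PCA was excluded, the line arguably discloses this, and PCA is not dropped from the pain outcome, since its duration and the switch to oral-only analgesics have their own lines. Longer PCA and no difference in amount per day are also different quantities and can both be true.

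Much of this stands. The second meaning cannot be ruled out, and the two results do not contradict each other. If the PCA drug were not an opioid, the conflict with the opioid category would fall away. The reply does not remove the problem, however. Durations do not answer the dosage element of 1.2.16, the footnote gives no sign that any drug is left out, and the reader cannot tell what the only amount result covers.

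A reader might go further and infer that opioid use is under-counted most in open RS, which would pull the comparison towards no difference or make eTEP look worse. The protocol does not support that. The parameter is a daily rate, and stay was longer in open RS too. A size might also be attached. For instance, equal 4-day windows, 1 against 2 PCA days inside the window, and nothing counted on those days give counted fractions of 3/4 = 0.75 and 2/4 = 0.50, an apparent shortfall of 1 − 0.50/0.75 = 33% in open RS. Equal windows do not fit the longer stay reported for open RS. With a 2-day eTEP window holding 1 PCA day (1/2 = 0.50), open RS with 2 PCA days is level at 4 days (0.50) and reversed at 5 days (3/5 = 0.60). Nor does the protocol say that paracetamol, anti-inflammatory drugs or other opioids stop while the pump runs.

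**Conclusion.** The point holds in a limited form. On the more natural reading, PCA drug is not in the numerator of the comparable parameter. The null result then concerns non-PCA analgesics only, does not answer the dosage part of the primary pain outcome, and cannot be read as equal opioid or total analgesic use. On the other reading, the defect is that the text does not say PCA drug is counted. Either way the 1.2.20 text needs correcting.

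The direction and size of any bias cannot be determined from the protocol. That would need the PCA drug, its amounts, and the PCA and stay durations by group, none of which is given. The conclusion that the null result is uninformative about total use does not depend on the direction. It rests on the exclusion reading and on the summary's own report that PCA duration differed between groups.

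**What to change.** Leave section 1.2.16 as it is. It already covers all analgesics, and editing a primary outcome after results are known would create a new problem.

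In the definition in section 1.2.20:

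1. State whether drug delivered by PCA is counted, and in which category. If it is already counted, this sentence is the whole change.
2. If it is not counted, take the PCA-delivered amounts from the medical records, add them to the relevant category, and re-run the comparison on the PCA plus non-PCA amount. Label this as a correction made after results were known, and show the non-PCA amount only as a component.
3. Where pump totals cannot be retrieved, label the category and the result as non-PCA analgesics, and do not present it as the analgesic-amount result.

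The cost is one further extraction from records that section 3.1.9 says are already the data source, and a re-run of one comparison. The downside is that some pump totals may be missing. The change is still timely: section 1.2.20 says there is no journal publication yet, and section 4.1.2 says the final protocol goes to the journal at submission.

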1.2.14 Sample Size

Planned:

- Group 1 (eTEP): 30 participants
- Group 2 (Rives-Stoppa, control): 30 participants

Actual:

- Group 1 (eTEP): 30 participants
- Group 2 (Rives-Stoppa, control): 30 participants

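### The comparable parameter counts opioid-containing combination products only as opioids, so their paracetamol or NSAID content is missing from its own category

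*Protocol*

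**What the plan says.** Postoperative pain management is one of two primary outcomes. Protocol 1.2.16 records it as "Modality (type, generic name), duration (days), dosage (grams or" milligrams, together with the number of administrations per day.

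The comparable parameter is defined in the footnote to the brief summary in 1.2.20. The three categories are: "Category 1 contained only paracetamol, category 2 contained all non-steroidal anti-inflammatory drugs, and category 3 consisted of all opioids". For products with more than one active substance the rule is: "A combination of active substances (in one analgesic) of which at least one was an opioid was seen as category 3". No split into components is described. The quantity is then formed per person: "For each participant the absolute amount of analgesics in each category was calculated between postoperative day one and the day before discharge". That total is divided by the number of days in the same window. The unit of the amount is not given.

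The result is one line: "No significant difference in 'comparable parameter'* for postoperatively administered analgesics irrespective of PCA between both groups". There are no figures by category or group, and nothing on how often combination products were used. The same summary reports a longer median stay and longer patient-controlled analgesia in the open group, and also: "Switch to only oral analgesics took longer in the open RS group".

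**The concern.** The categories are presented as drug classes, but the combination rule sorts by product. Two people who take the same paracetamol and the same opioid get different scores if one takes two separate products and the other a fixed combination. The first is credited in categories 1 and 3, the second in category 3 only. Category 1 or 2 then no longer measures exposure to its own class.

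This matters because the parameter is the reported between-group summary of analgesic quantity for a primary outcome. The rule is not a detail left for later: version 3 of the protocol states it, applies it and reports a result from it. With no breakdown shown, a reader cannot tell how far the rule shaped that result.

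**Working it through.** **Plan's own figure.** None is given for the parameter, so there is nothing to reproduce. The check is of the definition, followed by an illustration on assumed inputs.

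**Step 1: what follows without assumptions.** Category 1 holds paracetamol, category 2 NSAIDs, and an opioid combination goes wholly to category 3. So 100% of the non-opioid content of such a product is absent from category 1 or 2. This does not depend on the unit.

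**Step 2: if the amount is a number of doses (assumed counts).** Suppose the truth is 4 paracetamol and 2 opioid administrations per day. With 1 combination dose, category 1 reads 4 − 1 = 3. With 2 combination doses, it reads 4 − 2 = 2. Category 3 reads 2 in both cases and is not inflated.

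**Step 3: if the amount is product mass (assumed inputs).** Let P be true paracetamol and O true opioid in mg/day, s the share of opioid given in combinations, and r the mg of paracetamol per mg of opioid in the product. Then:

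- category 1 reads P − r·s·O
- category 3 reads O + r·s·O

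Take P = 3000 and O = 100, with r from 5 to 20. None of these comes from the protocol.

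| r | s | r·s·O | Category 1 (true 3000) | Category 3 (true 100) |
|---|---|---|---|---|
| 5 | 20% | 100 | 2900 | 200 |
| 5 | 50% | 250 | 2750 | 350 |
| 10 | 20% | 200 | 2800 | 300 |
| 10 | 50% | 500 | 2500 | 600 |
| 20 | 20% | 400 | 2600 | 500 |
| 20 | 50% | 1000 | 2000 | 1100 |

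For the combination doses alone, whole mass over opioid mass is (r + 1)/1, which is 6 at r = 5 and 21 at r = 20.

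**Step 4: between groups.** If both groups have the same true intake and the same share s, they shift alike and the category 3 ratio stays at 1.0. If the shares were 20% and 50%, the ratio would be 350/200 = 1.75, 600/300 = 2.0 or 1100/500 = 2.2, although true intake is identical. The protocol reports neither share.

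**Step 5: can the direction be inferred from the oral switch?** Only if an earlier switch means a larger share of days on oral drugs. Stay was also shorter after eTEP, so it need not. With assumed days, an eTEP switch on day 2 of 3 leaves 1/3 of the stay afterwards, and an open switch on day 3 of 6 leaves 3/6 = 1/2. Here the later switch goes with the larger oral share.

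**Step 6: after splitting by component.** The term r·s·O becomes zero and, in the illustration, both groups read 3000 and 100 mg/day. The real corrected values cannot be computed from the protocol.

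**The case against.** The rule is openly stated, applied identically to both groups, and consistent with 1.2.16. Sorting products by their opioid component is a recognisable convention. The unit is open, and the mass reading is far from certain: the same footnote uses the word amount for a number of days, and 1.2.16 records frequency as well as dosage. On a count, the inflation of category 3 disappears. The other in-hospital pain results (duration of patient-controlled analgesia, time to oral-only treatment) do not rest on this parameter.

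Most of this stands, and it limits the point. The loss from categories 1 and 2 nevertheless remains under either unit. Disclosure does not make those categories measure what their labels say.

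A reader might go further and infer that the rule works against eTEP and explains the null result, because eTEP participants moved to oral drugs sooner. The document does not support this. It does not say which combinations were used, by what route, how often or in which group, and the oral-switch result does not fix the share of oral days (Step 5). Nor should the 6- to 21-fold factor be read as an estimate: it needs the mass reading and assumed product ratios.

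**Conclusion.** The point holds as a defect of definition. In anyone given an opioid-containing combination, category 1 or 2 understates exposure to its own class by the full non-opioid content of that product. If the amount is product mass, the same content is also counted as opioid.

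The size depends on how often such products were used, which is not reported. The illustrated shifts (category 1 at 2900 to 2000 instead of 3000 mg/day, category 3 at 200 to 1100 instead of 100) rest wholly on assumed intakes, shares and ratios. If combinations were rare, the effect is negligible.

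Whether the effect differs between groups, which way it runs, and whether it bears on the reported absence of a significant difference cannot be determined from the protocol. The correction is worth making because it concerns the summary of a primary outcome, and version 3 states that no journal publication had yet been achieved.

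**What to change.** Make four changes to the definition in 1.2.20 and its result:

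1. Replace the combination rule so that each active substance of a combination product is credited to its own category: paracetamol to 1, NSAID to 2, opioid to 3.
2. State the unit of the amount. Use either the number of administrations per substance, or mass for paracetamol with a stated common scale for NSAIDs and for opioids. Raw milligrams summed across different NSAIDs or different opioids are not comparable and should not be used.
3. Recompute the parameter for all 60 participants (30 + 30) and restate the result by category and group.
4. Report the use of combination products by group beside it, so that a reader can judge how much the rule mattered.

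The generic names and doses to be recorded under 1.2.16 should suffice, assuming they identify the strength of each combination product. No new data collection is planned. The cost is some hours of recoding and the possibility that the reported result changes.

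### The only reported measure of analgesic amount is a daily mean over a window set by length of stay, so its non-significant result does not show similar consumption

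*Protocol*

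**What the plan says.** Protocol section 1.2.16 names two primary outcomes: length of hospital stay, and postoperative pain management. The second is recorded as type, duration, dosage and frequency of analgesics, with the hospital stay as its timepoint.

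The brief summary in section 1.2.20 gives four results on analgesia: PCA duration, time to oral-only analgesics, presence of prescription opioids at discharge, and the comparable parameter. Only the last is an amount. Its definition reads: "For each participant the absolute amount of analgesics in each category was calculated between postoperative day one and the day before discharge", and then "this amount was divided by the amount of days between postoperative day one and the day before discharge". There are three categories: paracetamol, non-steroidal anti-inflammatory drugs (NSAIDs) and opioids. Of the third, the text says "category 3 consisted of all opioids" and "A combination of active substances (in one analgesic) of which at least one was an opioid was seen as category 3".

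The parameter is reported as not significantly different "for postoperatively administered analgesics irrespective of PCA between both groups". The same summary states: "Median length of hospital stay was longer in the open RS group" and "Median duration of patient-controlled analgesia was longer in the open RS group". On timing, it records: "Date of the first journal publication of results: Not yet achieved".

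**The concern.** A daily mean looks like an adjustment for length of stay, but it adjusts only for the count of days. A patient discharged on day three is averaged over days one and two; a patient discharged on day five is averaged over days one to four. If analgesic use changes over recovery, these two patients get different values even when they took the same amount on each day that both were in hospital. Since median stay was longer in the open arm, that arm is on average judged on later recovery days.

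At stake is how a null result on a primary outcome is read. A non-significant difference in amount invites the conclusion that consumption was similar, and this measure cannot carry that conclusion. Three gaps in the definition add to the difficulty:

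- No unit or opioid equivalence is stated, so a total across different opioids cannot be interpreted.
- The paracetamol or NSAID part of an opioid combination product is not counted in its own category.
- The wording on PCA does not say whether PCA doses are in the total, although PCA ran longer in the open arm.

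**Working it through.** The protocol gives no stay lengths, daily amounts or standard deviations, so there is no figure of its own to reproduce. The check applies its definition to assumed inputs.

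**Definition.** With the operation on day 0 and discharge on day L, the window is days 1 to L−1. Let use on day d be proportional to r^(d−1), with the same r in both arms. Each patient's value is the mean of r^(d−1) over d = 1 to L−1.

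**One patient per arm, use falling 20% per day (r = 0.8).**
- L = 3: (1 + 0.8)/2 = 0.900
- L = 5: (1 + 0.8 + 0.64 + 0.512)/4 = 0.738
- Ratio: 0.738/0.900 = 0.820, with identical use on every shared day

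**Overlapping stays (assumed).**
- eTEP, L = 2/3/4/5/6 days in 20/40/20/10/10% of patients (median 3)
- Open, scenario A, L = 3/4/5/6/7 in 10/20/40/20/10% (median 5)
- Open, scenario B, L = 2/3/4/5/6 in 10/20/40/20/10% (median 4)

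The arm value is the weighted mean of the patient values. For r = 0.7 the patient values at L = 2 to 7 are 1, 0.850, 0.730, 0.633, 0.555 and 0.490, which give:
- eTEP: 0.2×1 + 0.4×0.850 + 0.2×0.730 + 0.1×0.633 + 0.1×0.555 = 0.805
- Open A: 0.1×0.850 + 0.2×0.730 + 0.4×0.633 + 0.2×0.555 + 0.1×0.490 = 0.644
- Ratio: 0.644/0.805 = 0.80

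Open/eTEP ratio with identical day-by-day use:

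| Daily change in use | Every stay 5 v 3 days | Overlapping, medians 5 v 3 | Overlapping, medians 4 v 3 |
|---|---|---|---|
| −30% | 0.745 | 0.801 | 0.925 |
| −20% | 0.820 | 0.861 | 0.950 |
| −10% | 0.905 | 0.928 | 0.975 |
| flat | 1.000 | 1.000 | 1.000 |
| +10% | 1.105 | 1.078 | 1.025 |

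**Read the other way.** The daily excess in the open arm that would leave the mean parameter equal is 1/ratio − 1. For falls of 30%, 20% and 10% it is 24.9%, 16.1% and 7.8% (overlapping, 5 v 3), or 8.2%, 5.3% and 2.6% (overlapping, 4 v 3).

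**Effect on a test.** A simulation used 30 v 30 patients, mean stays of 3 v 5 days (2 + Poisson), between-patient log-SD 0.5, a two-sided Mann-Whitney test at 0.05 and 1,500 runs per scenario. With truly equal daily use, the parameter rejected in 28% of runs (20% fall) and 50% (30% fall). With true daily use 1.25 times higher in the open arm, it rejected in about 6% under either fall. A fixed window of days one and two rejected in about 4% to 7% and about 36% to 38% respectively. That comparator is idealised: it takes day-two amounts as known even for patients discharged on day two.

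**The case against.** The strongest reply is that the window follows the protocol. Section 1.2.16 sets the timepoint for pain management as the hospital stay, and averaging over nearly all of the stay implements it. A fixed early window answers a different question. This stands, and is a reason to keep the parameter rather than replace it.

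Second, the size is entirely assumed. With medians of 4 v 3 the distortion is only 2.5% to 7.5%, and with flat use it is zero. One rate of change is applied to all drugs, although the three categories are separate parameters, and discharge is treated as unrelated to use. With 30 per arm, even the fixed window had only 36% to 38% power for a 1.25-fold difference, so a null result at that size would be unsurprising with either measure. All this stands: the calculation shows what the definition permits, not what happened.

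Third, the protocol claims no equivalence, and longer PCA and a later oral switch in the open arm are reported beside the parameter. That limits the harm, but those results are durations, not amounts.

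Two stronger readings are tempting. A reader might infer that the parameter hid greater use after open surgery. The documents do not support this: they give no daily profile, and rising use would reverse the direction. A reader might also infer that opioids were added without potency conversion, or that PCA doses were left out. The text neither describes nor denies conversion, and its PCA wording is open either way. The supportable statement is that these matters are not stated.

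**Conclusion.** The concern holds as a limitation of the measure. The reported amount comparison depends on length of stay, which differed between the arms, and is fair by recovery day only if daily use is roughly flat. That follows from the definition and the reported medians, without outside data. The illustrative ratios of about 0.75 to 0.98 rest on assumed stays and assumed falls of 10% to 30% per day; the true size and direction are unknown. The non-significant result is therefore not evidence of similar consumption, nor is it evidence of a hidden difference. The unstated unit, opioid equivalence and PCA handling are gaps to fill rather than demonstrated errors. The allocation of combination products is stated, and should be examined in the sensitivity analysis.

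**What to change.** Before journal publication:

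1. Keep the comparable parameter as reported, and state that its window depends on length of stay and that a null result on it does not establish similar use.
2. Add a sensitivity analysis, clearly labelled post hoc, that compares amount per category over the same early postoperative days in both arms, or models daily amount by group and postoperative day. The label matters: results are already posted, and an unlabelled new comparison would look like outcome re-selection.
3. In that analysis, express opioids in a common stated unit, split combination products into their components, and say whether PCA doses are included. State the unit and the PCA handling for the existing parameter too.

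The cost is modest, since sections 1.2.16 and 3.1.9 say that type, dosage, frequency and duration are collected for all participants. There are downsides. A conversion table must be chosen and stated, and PCA doses may need a further check of the records. The common window may be only one or two days if some patients leave early: in the assumed eTEP distribution, 20% have day one as their last counted day. A longer window, or the model, needs an explicit assumption about the days after discharge.
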